#### Focus B: Understand how Let's Talk format impacts ease of use

Introduction: Now I'm interested in learning more about how easy or difficult it was to use the workbook as a "paper"/PDF format, as well as any suggestions you have for improving its design.

1. Would you prefer an online version of the workbook? Why or why not?
2. What additional materials, if any, would enhance your use of the workbook?
3. Does the format (e.g. paper-based) of the work workbook create any barriers to its use?
4. Will the format (e.g. paper-based) of the workbook affect your ability to use the workbook?

#### Theme #2: Demand

##### Focus A: Understand Let's Talk value to patients

Introduction: I'm also interested in hearing about how the workbook was valuable to you, if it was, and how it impacted the process of communicating with your family members.

#### Interview Questions:

1. Is the workbook effective in enhancing your knowledge of cascade screening (the process of testing family members for Lynch syndrome)?
2. What positive or negative effects have you experienced in using the workbook?
3. Would you recommend the workbook to other patients? Why or why not?

#### Theme #3: Reach

##### Measure #1: Intention to Discuss Lynch Syndrome

Question: On a scale of 1 to 5, 1 being extremely weak and 5 being extremely strong, choose the number that represents your intention to discuss Lynch Syndrome with your relatives. Explain how you arrived at your chosen number.

OR

**Measure #2A: Number of Relatives Contacted**

Question: How many relatives have you contacted regarding your Lynch Syndrome diagnosis after using the workbook?

Measure #2B: What was your overall impression of the conversation with your relative? What went well and what could have gone better?

**Measure #3: Number of Relatives Who Sought Genetic Testing**

Question: Of the relatives you contacted, how many have sought genetic testing?

Conclusion: Is there anything else you'd like to share before we wrap up today?

**9.2. Patient Acceptability Electronic Survey Segment**

Acceptability: Please rate how much you agree with the following statements  
(1 – Strongly disagree to 5 – Strongly agree)

The workbook was easy to use.

The workbook exercises were understandable.

I enjoyed using the workbook.

The workbook was helpful in understanding Lynch Syndrome and the importance of family genetic testing.

The workbook was helpful in communicating my diagnosis and information about genetic testing with relatives.

Completing the workbook exercises took an acceptable amount of time.

Overall, I am satisfied with the workbook.

**9.3. Patient Self-Efficacy Electronic Survey Segment**

Self-Efficacy: Please rate how confident you are in your ability to do the following tasks.

Identify relatives that are good candidates for genetic testing for Lynch Syndrome.

Plan strategies to communicate with relatives about Lynch Syndrome.

Share your Lynch Syndrome diagnosis with a relative.

Explain what Lynch Syndrome is and the associated risk of cancer.

Explain the benefits and risks of genetic testing for Lynch Syndrome to relatives.

#### 9.4. Patient Knowledge and Perceived Knowledge Electronic Survey Segment

Please answer the following questions about Lynch Syndrome. Then please rate your confidence that you chose the correct answer for each question. The scale for confidence is Very Sure, Somewhat Sure, Neither Sure nor Unsure, Somewhat Unsure, and Very Unsure.

(1) Having Lynch Syndrome means you have a \_\_\_\_\_ of developing certain types of cancer compared to people who don't have Lynch Syndrome.

Higher risk

Lower risk

Equal risk

(2) Lynch Syndrome is a genetic condition which means:

All members of a family will have Lynch Syndrome.

Lynch Syndrome can be passed down between generations of a family.

Other family members are not at risk for Lynch Syndrome if a family member is diagnosed with Lynch Syndrome.

(3) What are the most common types of cancer associated with Lynch Syndrome?

Skin and bone cancer

Brain and stomach cancer

Colorectal and endometrial/uterine cancer

(4) What family members should I discuss my Lynch Syndrome diagnosis with?

No family members. I should only discuss my diagnosis with my doctors.

My nieces, nephews, aunts, uncles, and cousins

My parents, children, brothers, and sisters

(5) The best way to manage the risk of cancer after a Lynch Syndrome diagnosis is:

Talk to your doctor about screening for cancer at a younger age and possible surgical options to prevent cancer.

There is nothing I can do to prevent getting cancer if I have Lynch Syndrome.

Continue with my usual care and bring up my Lynch Syndrome diagnosis if I get diagnosed with cancer.

(6) Why should people diagnosed with Lynch Syndrome talk to their relatives about their diagnosis?

So their relatives can start increased screening for Lynch Syndrome related cancers.

So their relatives can teach other people about what Lynch Syndrome is

So their relatives can seek genetic testing to learn their own Lynch Syndrome

status and make the best choices for their health.

(7) How do relatives benefit from receiving genetic testing for Lynch Syndrome?

They will know if they should talk with their providers about ways to manage Lynch Syndrome and if they should talk to their family members about Lynch Syndrome risks.

They will know when they should start receiving treatment for cancer.

They will know if they should start annual screenings for all types of cancer.

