#### 4.2. Study Recruitment and Activities

The recruitment goal for genetic counselors is up to 5 genetic counselors. The recruitment goal for patients with Lynch Syndrome is 15 total patients between OSU, UNC, and LSI. There is no minimum or maximum number of patients that can be enrolled at each site up to the goal of 15 patients total.

At OSU and UNC, the co-PI or another member of the research team will contact genetic counselors who work with Lynch Syndrome patients via email and notify them of the study opportunity and provide an information sheet. Interested genetic counselors will use the workbook with their Lynch Syndrome patients as a support tool for their standard cascade screening. The genetic counselors will provide the workbook to patients likely to test positive for Lynch syndrome or patients who have already been confirmed to have Lynch syndrome. If the patient is positive for Lynch syndrome, during a counseling call/appointment, the genetic counselor will complete the first prompt of the workbook to identify family members with the patient and explain the other sections of the workbook. Patients will complete the other sections of the work independently. The genetic counselor will notify the patient that the workbook creators are interested in hearing feedback on the workbook use and if the patient is interested, the genetic counselor will send the name, phone number, and email address of the patient to the UNC research team via secure email.

Through the LSI Facebook page, the study team will post an advertisement for patients recently diagnosed with Lynch Syndrome. Interested patients will reach out to the UNC research team by emailing the address posted in the study advertisement.

[figure not shown]
For all patients referred by a genetic counselor or self-referred, the UNC research team will schedule and complete a study enrollment call to answer questions, confirm eligibility, and document informed consent to participate in a follow up interview and survey. For patients directed to the study from the LSI Facebook page advertisement, the UNC research team will provide the workbook following the enrollment call and the participant will complete the activities in the workbook independently.

The UNC research team will complete the follow up interview and survey with patients approximately 4 weeks after they received the workbook from their genetic counselor.

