All patient information will be tracked in a project in UNC's REDCap. All follow up interviews for patients will be conducted via Zoom. All follow up surveys for patients will be conducted electronically in REDCap.

For questions specifically related to genetic counseling or care management, patient participants should contact their site-specific genetic counselor or personal healthcare provider. For all other questions and concerns at any point in the study, participants recruited from OSU or UNC should contact the UNC research team. Questions about study eligibility and responsibilities should be directed to the UNC research team. If participants have questions or concerns about their rights as a research subject, or if they would like to obtain information or offer input, they can also contact the UNC Institutional Review Board at [contact] or by email to [IRB\\[contact]](mailto:[contact]).

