#### 4.5. Intervention Description

The educational workbook is in a PDF format. The workbook contains a series of lessons and exercises on the following topics:

What is Lynch Syndrome?

Why should I tell my family members about Lynch Syndrome?

Who is at risk for Lynch Syndrome and who should I reach out to?

Create a list of first-degree relatives at risk for inheriting Lynch Syndrome

What should I tell my family members about Lynch Syndrome?

Create a script for discussing Lynch Syndrome with family

What are common concerns family members might express?

How should I tell my family members about Lynch Syndrome?

Create a plan to reach out to each family member

Create goals for talking to family members

What if my conversation with family didn't go well?

What are common terms and questions about Lynch Syndrome?

How can I manage having Lynch Syndrome?

Where can I find additional information about living with Lynch Syndrome

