#### 4.6. Follow Up

After a genetic counselor has provided the contact information of an interested patients or the patient has directly contacted the research team by email, the UNC research team will reach out to the patient in approximately 1 weeks to gather informed consent and will conduct a follow up interview and survey after approximately 4 weeks.

All interviews will be completed through Zoom using a semi-structured interview guide developed by the research team based on the Consolidated Framework for Implementation Research The interviews will be conducted by the research assistant and a trained interviewer and recorded. The recordings will be transcribed for qualitative template analysis to identify major themes.

During the follow-up session, participants will also complete an electronic survey to assess the following feasibility concepts: acceptability of workbook, self-efficacy, Lynch Syndrome knowledge, Lynch Syndrome perceived knowledge, cost of workbook use.

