## 7. STUDY MANAGEMENT

### 7.1. Data Management/Audit

Qualitative interviews will be conducted via Zoom and recorded using Zoom. Video will not be used through Zoom interviews. The recording will be downloaded, transcribed and deidentified, and stored on a secure network drive. The research assistant will also take notes during the interviews and the notes will be stored on a secure network drive. The final codebook of themes and subthemes identified in the interviews will be stored in a Microsoft Word document.

The electronic survey will be administered through REDCap and the collected data will be stored in the REDCap system. The survey results will be exported and loaded into STATA for statistical analysis. Exported data files will be stored on a secure network drive.

The research will receive a limited waiver of HIPAA authorization to allow genetic counselors and the research team to access PHI necessary for the recruitment of Lynch Syndrome patients. Specifically, the waiver will approve access to patient names, patient ID numbers for UNC patients, telephone numbers, email addresses, ages, diagnoses, and dates of diagnosis. Participant contact and enrollment information will be collected and stored in REDCap. Contact and identifying information for all patients who are referred to the UNC research team by their genetic counselor will be collected and stored in REDCap. The data for patients who decline to participate or are found ineligible during enrollment or withdraw from the study at a later point will remain stored in REDCap. The names and contact information of participants

and patients who were contacted but not enrolled or withdrew from the study, along with linkage codes, will be destroyed by the PI after the study is complete.

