## 9. APPENDICES

### 9.1. Patient Qualitative Semi-Structured Interview Guide

Theme #1: Practicality

Focus A: Understand Let's Talk complexity

Interview Questions:

1. Now that you have used the workbook, what did you think about it?
  - a. What did you like?
  - b. What did you dislike?
2. How complex or easy did you find it was to use "Let's Talk"?
3. How long did it take you to complete the exercises in the workbook?
  - a. For patients recruited through LSI: The first prompt covered identifying your first-degree relatives. How did identifying your relatives go? Could anything have improved the process of identifying relatives to contact?

4. How did you feel about the length of the workbook? (too long, too short, just right?)
5. Did you seek help from anyone when you used the workbook?
6. Was the organization of the exercises logical?
  - a. Would you change the order of the workbook sections?
7. Was there any part of the workbook you found difficult to understand or complete? Please explain.

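### The knowledge items are answered in a remote session with no closed-book instruction and no record of look-up, so two of the four tested scores may be partly open-book

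*Combined protocol and SAP*

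**What the plan says.** **Delivery.** Section 4.2 states "All follow up surveys for patients will be conducted electronically in REDCap" and "All follow up interviews for patients will be conducted via Zoom". Section 4.6 places the survey in the same session as the interview: "During the follow-up session, participants will also complete an electronic survey to assess the following feasibility concepts". On timing and staffing, Section 4.2 says "The UNC research team will complete the follow up interview and survey with patients approximately 4 weeks after they received the workbook". Section 7.1 adds "Video will not be used through Zoom interviews".

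**Access to the workbook.** Section 4.5 states "The educational workbook is in a PDF format". Cost question 9 in Section 9.5 asks whether the patient used it on a screen or printed it. No section describes its return or closure before the survey. Its listed topics include what Lynch Syndrome is, who is at risk, whom and why to tell, and how to manage the condition. The items in 9.4 test largely the same ground.

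**Instruction and scoring.** The instruction in 9.4 is "Please answer the following questions about Lynch Syndrome. Then please rate your confidence that you chose the correct answer for each question", followed by the confidence labels. Section 4.7.2 reads 4/7 or more as moderate to high knowledge, and 21 or more as moderate to high perceived knowledge. It compares both scores, along with acceptability and self-efficacy, with their thresholds by one-sample Wilcoxon signed rank tests. Neither alpha nor sidedness is stated.

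**The concern.** Section 4.7.2 treats the seven-item score as the knowledge of workbook users. That reading is natural if the answers come from memory. If some patients consult the workbook while answering, the score measures in part whether the answer could be found. Look-up can be expected to push the knowledge score up. Because each confidence rating follows its item, it can raise perceived knowledge too. Two of the four tested scores are exposed, both in the direction that favours the workbook.

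The study has one arm and post-intervention surveys only, so no baseline or control group would reveal the shift. Nothing collected would let the analyst identify the patients concerned. Cost questions 11 and 12 in Section 9.5 ask about other resources used after the workbook, not about sources used while answering. The results are meant to inform a larger grant application (Section 1.3), so a flattering knowledge score could be carried forward.

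**Working it through.** **No figure to reproduce.** The 15 patients are justified by thematic saturation (Section 4.7.1). The plan gives no power or expected score for the knowledge test.

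**Check of the text.** Sections 4.2, 4.6, 4.7.2, 7.1 and 9.4 were read for a closed-book instruction, a time limit, observation of the patient, or a question on sources used. None was found.

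**Illustrations of size.** From the documents: 7 items, 3 options each, threshold 4, n = 15. Assumed: the look-up rates, independent items of equal difficulty, a looked-up item always correct, and alpha 0.05.

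1. *Shift in the mean.* Five patients move from 4 to 7 and ten stay at 4: 5 × 3 / 15 = 1.0 point. The ten zero differences drop out of the signed rank test. Five positive differences give an exact one-sided p of (1/2)^5 = 1/32 = 0.031, or 2/32 = 0.0625 two-sided. Placing the other ten at exactly 4 is a favourable choice for showing the effect.

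2. *One patient.* With k items looked up and the other 7 − k guessed at 1/3, the chance of reaching 4/7 is P(Bin(7 − k, 1/3) ≥ 4 − k):

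| k looked up | Mean score, k + (7 − k)/3 | Chance of 4/7 or more |
|---|---|---|
| 0 | 2.33 | 0.17 |
| 1 | 3.00 | 0.32 |
| 2 | 3.67 | 0.54 |
| 3 | 4.33 | 0.80 |
| 4 | 5.00 | 1.00 |

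3. *The group test.* Let recall average 4/7, and let a fraction L of the items otherwise missed be looked up. The mean score is 4 + 3L. The last two columns come from 4,000 simulated samples of 15 (Wilcoxon test against 4, normal approximation, zeros dropped):

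| L | Mean score | Finds above 4, one-sided | Two-sided, upper side |
|---|---|---|---|
| 0 | 4.00 | 5% | 2% |
| 10% | 4.30 | 21% | 13% |
| 25% | 4.75 | 71% | 56% |
| 50% | 5.50 | >99% | 99% |

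If recall averages 3.5/7, below the threshold, L = 25% gives a mean of 3.5 + 3.5 × 0.25 = 4.375 and about 30% one-sided. L = 50% gives 5.25 and about 98%.

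4. *When it makes no difference.* In this model the test depends only on the overall proportion correct. If recall alone averaged 5.5/7, the test would already exceed the threshold more than 99% of the time (one-sided), and look-up would not change the conclusion. The bias matters for the test only when true recall lies near or below 4/7.

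5. *Perceived knowledge.* A middle rating on all seven items gives 7 × 3 = 21, exactly the threshold. If look-up moved two of those ratings from 3 to 5 (assumed), the total would be 21 + 2 × 2 = 25.

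**The case against.** **Much of the setting is inferred.** The documents do not say whose device is used or that the workbook is open during the survey. The interview guide does ask "Would you change the order of the workbook sections", which could prompt a patient to have it to hand. But the guide is retrospective, does not ask anyone to bring the workbook, and the order of interview and survey is not stated. This stands, so the point rests only on patients having been given the workbook.

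**The no-video rule is written for interviews.** It appears in text on recording and transcription. It reaches the survey only because both take place in one session, and Section 4.2 suggests that staff may be on the line. A reader might infer an unsupervised test taken with the workbook open, and the documents do not support that. Staff listening by audio alone, however, could not see whether it was open.

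**The screens and scripts are not printed.** The appendix gives survey segments, not REDCap paging or staff wording. A closed-book instruction may exist there. This stands, and it is why the point is confined to the printed instructions.

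**Cueing between items is minor.** The stem of item 7 hints at the answer to item 6, but only helps if patients can see ahead or go back. Another option in item 6, on increased screening, remains plausible.

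**A closed-book score would not prove learning either.** With no baseline or control, in patients diagnosed up to 365 days earlier, it could not separate what the workbook taught from what was already known. This stands. The gain from closing the book is narrower: the score would then better reflect what patients know.

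**Conclusion.** The point holds in a limited form. The printed plan neither asks for recall nor records look-up, in a remote session with patients who have been given the relevant content. The knowledge and perceived-knowledge scores may therefore be partly open-book and biased upward.

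The size is unknown. Under the assumptions shown, look-up of a quarter of otherwise-missed items would raise the chance of a favourable one-sided result from about 5% to 71% when recall averages exactly 4/7. It would make essentially no difference if recall were already well above the threshold.

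A reader might go further and conclude that patients did look answers up, or that the knowledge result is invalid. The documents support neither: they contain no evidence of look-up. The study's qualitative component and its sample size are unaffected. This is an inexpensive improvement to how two scores are collected and read.

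**What to change.** For surveys still to be completed:

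- Add to the 9.4 instruction: *Please close the workbook and other sources and answer from memory.*
- Add after item 7: *Did you look at the workbook or another source for any answer? (yes / no)*
- Summarise knowledge and perceived knowledge with and without patients who answer yes. With 15 patients, treat this as descriptive.
- Optional and minor: show one item per screen with no back button, because of the hint from item 7 to item 6.

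For surveys already completed, leave the data as they are and describe both scores as possibly open-book. This may apply to some or all patients, since the version 7 summary of changes describes recruitment in the past tense.

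The cost is two lines of survey text and, if wanted, a REDCap setting. There are three downsides. Self-report of look-up is imperfect. The change needs IRB approval before use (Section 7.4). A change mid-study would mix two modes of administration among 15 patients, so record which version each patient completed.

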#### 9.5. Patient Workbook Costs Electronic Survey Segment

We are interested in understanding what time and resources are necessary to use the workbook. The next set of questions are intended to evaluate the time and resources needed to use this workbook starting from the genetic counseling appointment when you first received the workbook.

(1) Your genetic counseling appointment took place virtually. Did you have to purchase any new tools or resources to access your appointment? If yes, please describe.

(2) How far away do you live from your genetic counselor's physical office? Please estimate the distance in miles and the time it would have taken you to travel to and from your genetic counselor's physical office.

(3) How long did you use the workbook with your genetic counselor? (Please round your answer to the nearest 15 minutes.)

(4) Did you have to take time off work to talk with your genetic counselor?

(5) How many hours, if any, did you take off work to meet with your genetic counselor to learn about the workbook?

(6) After your genetic counseling appointment, how long did it take you to go through the workbook exercises? (Please round your answer to the nearest 15 minutes.)

(7) Did you take any time off work to use the workbook?

(8) How many hours, if any, did you take off work to use the workbook?

(9) Did you use the workbook in a virtual format (e.g. using a computer, tablet or phone) or did you print the workbook and fill it out by hand?

(10) Which pages of the workbook did you print? Please describe (e.g. all pages, pages 1-5, etc.)

- (11) After using the workbook, did you spend any additional time using other resources for Lynch Syndrome that were mentioned in the workbook?
- (12) How long did you spend using the extra resources mentioned in the workbook? (Please round your answer to the nearest 15 minutes.)
- (13) How many first-degree relatives did you communicate with after using the workbook?
- (14) Did you take any time off work to communicate with your relatives?
- (15) How many hours, if any, did you take off work to communicate with your relatives?
- (16) For each relative that you contacted, please list (1) how you communicated with them and (2) how long the entire communication process took from initial contact to follow up. Please consider time spent planning, communicating, and following up with relatives.

Planning time refers to time spent coordinating/Preparing for communication with your relatives including activities such as arranging time for a phone call or traveling to see a family member.

Communication time refers to time spent telling your family member about your Lynch Syndrome diagnosis. Time might be spent talking to your relative over the phone or through a video chat.

Follow up time refers to additional time spent assisting your relatives after your initial conversation informing them of your diagnosis. For example, you might have spent time sending them additional resources about Lynch Syndrome or connecting them to a genetic counselor.

Example Scenario: I spent 10 minutes texting my sister to arrange a time to talk on the phone. I called her and we talked for 45 minutes during which I told her about my Lynch Syndrome diagnosis and explained why she should get tested. She asked for additional materials to learn about Lynch Syndrome, so after the call, I spent 20 minutes emailing additional resources to her. In the text box, I would list Text/Phone Call/Email as the method of communication, 10 minutes of planning time, 45 minutes of communication time, and 20 minutes of follow up time.

- (17) For each relative that you contacted, please describe your use (if any) of the following resources: (1) transportation, (2) Supplies, (3) Food & Drink, (4) Other.

Example: For my parent, I drove 30 miles total to and from my parent's house.

I also printed out 3 sheets of information on Lynch Syndrome to give to my parent.

(18) What was your preferred method of communication with your family members and why?

(19) If there were any unexpected costs that you had to pay in using the workbook, please describe in the text box.

How old are you?

- 18-25 years old
- 26-35 years old
- 36-45 years old
- 46-55 years old
- 56 years old or older

What is your sex?

- Male
- Female
- Other, please specify\_\_\_\_\_

What is your annual income?

- Less than \$20,000
- \$20,000 - \$34,999
- \$35,000 - \$49,999
- \$50,000 - \$64,999
- \$65,000 - \$79,999
- \$80,000 or greater

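### The cost survey in 9.5 starts from a counseling appointment that, under 4.2, did not deliver the workbook to LSI participants, so some cost answers can be misattributed and item 6 is not comparable between recruitment routes

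*Combined protocol and SAP*

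**What the plan says.** **Delivery of the workbook (4.2).** There are two routes.

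- Counselor route (OSU and UNC): "the genetic counselor will complete the first prompt of the workbook to identify family members with the patient", explains the other sections, and leaves the patient to do those alone.
- LSI route: "For patients directed to the study from the LSI Facebook page advertisement, the UNC research team will provide the workbook following the enrollment call". These patients then work through it on their own.

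Section 3.1.4 admits members of the LSI Facebook page as an alternative to patients under a study-site counselor, so an LSI participant need not be under one.

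**Cost survey (9.5).** There is one printed version for all patients. The preamble counts costs "starting from the genetic counseling appointment when you first received the workbook". Item 1 opens with a statement: "Your genetic counseling appointment took place virtually". Item 2 asks about distance and travel time to the counselor's office, and item 4 about time off work to talk with the counselor. Item 3 asks "How long did you use the workbook with your genetic counselor". Item 5 asks how many hours "did you take off work to meet with your genetic counselor to learn about the workbook". Item 6 asks "After your genetic counseling appointment, how long did it take you to go through the workbook exercises".

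**Use of the answers.** Section 1.1 lists economic impact among the things to be understood. Section 4.7.2 measures the cost of workbook use through 19 questions and gives no threshold, test or estimator for it.

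**The concern.** Sections 4.2 and 9.5 are both current text, and they describe different ways of receiving the workbook. The interview guide (9.1) has a probe written for LSI participants about the first prompt. The printed cost survey has no LSI wording and no not-applicable option.

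Three errors could follow when the cost data are summarized:

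- An LSI participant who had ordinary genetic counseling answers items 1, 2 or 4 about it, and the answer is counted as a workbook cost.
- A zero on item 3 or 5 is averaged in as though counselor delivery had taken place at no cost.
- Item 6 is pooled over routes although it covers different work on each.

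Section 4.7.2 has no rule that would prevent any of these.

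**Working it through.** **1. The plan's own figure.** Section 4.7.2 states 19 cost questions. The numbered items in 9.5 run from (1) to (19), so the count is reproduced.

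**2. Items sorted by what they presuppose.**

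| Items | Count | Meaning for an LSI participant under 4.2 |
|---|---|---|
| 1, 2, 4 | 3 | Counseling in general; normally unrelated to workbook delivery |
| 3, 5 | 2 | Counselor time tied to the workbook; usually zero or blank |
| 6 | 1 | Answerable, but timed from the appointment |
| 7 to 19 | 13 | No mention of a counselor |

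Check: 3 + 2 + 1 + 13 = 19. Items worded around a counselor: 6 of 19 (31.6%). Items tying counselor time to the workbook: 2 of 19 (10.5%).

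**3. Item 6 by route.** Let *p* be time on the first prompt, *e* the counselor's time explaining the other sections, and *r* time on the remaining exercises.

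- Counselor route: item 3 = *p* + *e*; item 6 = *r*.
- LSI route: item 3 = zero or not applicable; item 6 = *p* + *r*.

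If *p* and *r* were equal on both routes, item 6 would still be larger by *p* for LSI participants. The sum of items 3 and 6 is *p* + *e* + *r* against *p* + *r*. It differs only by *e*, which is real time spent on the counselor route, so the sum is the better comparison. The documents give no value for *p*, *e* or *r*.

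**4. Zeros on item 3.** Let *k* be the number of LSI participants among the 15. It is not given, so the values below are assumptions. Suppose all 15 answer, every LSI answer is zero, and counselor-route patients average *t*. A pooled mean would then be *t* × (15 − *k*)/15.

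| *k* (assumed) | Counselor-route patients, 15 − *k* | Pooled mean as a share of *t* |
|---|---|---|
| 5 | 10 | 10/15 = 0.67 |
| 10 | 5 | 5/15 = 0.33 |
| 14 | 1 | 1/15 = 0.07 |
| 15 | 0 | *t* cannot be estimated |

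The third column is the effect of reading zeros as free delivery. It disappears once those answers are coded as not applicable. The second column reflects only the recruitment mix and would be the same under any wording. The plan does not say that a mean will be used, so this is an illustration.

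**5. Which *k* is likely.** The version 7.0 entry in the summary of changes says that LSI recruitment was prioritized and that no OSU patients were recruited. It does not give the number referred by UNC counselors. It points to a high *k* without fixing it.

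**The case against.** **Scarcity is not caused by the wording.** A reader might infer that items 1 to 5 will yield little workbook cost data because the survey was not adapted. The documents do not support that. Counselor-delivery data will be few because few patients may come by that route, and a perfectly worded survey would have the same 15 − *k* respondents. This objection stands. What the wording causes is misattribution and non-comparability.

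**Five items are not simply lost.** A reader might also infer that LSI answers to items 3 and 5 can only be zero or blank, so that 5 of 19 items carry no workbook cost and should be discarded. That is too absolute. Section 4.2 does not bar LSI participants from taking the workbook to their own counselor, and the interview guide asks whether they sought help from anyone. A non-zero answer to item 3 or 5 could be a genuine workbook cost, and blanket exclusion would lose it. Item 2 asks a hypothetical travel time, and 4.2 places counselor-route counseling within standard cascade screening. Items 1, 2 and 4 may therefore be usual care on both routes. This also stands.

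**Deployment and stakes.** The survey runs in REDCap, which may branch by route. Section 9.5 prints no skip logic even for items 10 and 12, which would need it, so its absence on paper proves nothing. Section 2 names feasibility as the primary question and lists no secondary objectives. Interview question 3 asks about exercise time without mentioning a counselor, which gives a partial backstop for item 6. It is not an exact match for items 3 plus 6, because item 3 can include explanation.

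**Items 7 to 19.** These do not mention a counselor, but the preamble governs them too, and items 14 to 17 have no workbook start point of their own. Correcting the preamble covers this.

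None of these points removes the conflict between 4.2 and 9.5.

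**Conclusion.** The inconsistency is real and minor. For LSI participants the printed survey has a false start point, invites answers to items 1, 2 and 4 that could be miscounted as workbook costs, and makes zeros on items 3 and 5 ambiguous. Item 6 covers different work on each route. Six of 19 items are worded around a counselor, and two of those tie counselor time to the workbook.

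The effect is limited to descriptive cost summaries. The four scales compared with thresholds by Wilcoxon tests do not use 9.5. The overall size and direction of any bias cannot be computed, because the plan gives no cost estimator, no route split and no item times. Pooling over routes matters only if both routes contribute patients (*k* from 1 to 14). The conclusion assumes that the survey is administered as printed; if REDCap branches by route, what remains is a correction to the printed text and the need for route-specific reporting.

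**What to change.** **If the survey is still open**

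- Reword the preamble so that costs count from the time the patient first received the workbook.
- Reword item 6 along these lines: *Since receiving the workbook, and leaving out any time with a genetic counselor, how much time have you spent on its exercises?*
- Keep items 1 to 5 visible to everyone, with a not-applicable choice for patients who neither received nor used the workbook with a counselor.
- Remove the assertion in item 1 that the appointment was virtual.

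**If data are already collected**

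- Code zero or blank LSI answers to items 3 and 5 as not applicable.
- Keep any non-zero answer that describes using the workbook with a counselor.
- Do not count LSI answers to items 1, 2 and 4 as workbook costs.
- Footnote that item 6, as printed, has a different start point by route.

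**In either case**

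- Report costs by recruitment route, with the number answering each item.
- Report items 1, 2 and 4 separately as possible usual care.
- Compute total workbook time as item 3, if any, plus item 6.

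If REDCap already branches by route, correct the printed wording and keep the route-specific reporting.

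The cost is low: a few lines of survey text, or a coding and reporting note. No extra patients or data are needed. The downside is that the counselor-delivery items will be reported on few or no patients.
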